(1) Due to restrictions associated with the COVID-19 pandemic, this study will be delivered in a remote format. Enrolled families will complete surveys via an electronic device connected to the internet, and intervention sessions will similarly be offered in a virtual (phone or video conferencing) format. When restrictions associated with the COVID-10 pandemic are eased, the survey, behavioral, RSA, and intervention components of this study will be conducted in research laboratories at the Frances Payne Bolton School of Nursing and the Department of Psychology at Case Western Reserve University. The intervention session component of this study will be conducted at private community locations (e.g., library meeting rooms) that are convenient for enrolled study participants once covid-19 restrictions are eased. (2) Using an existing collaboration with the Cleveland Metro School District, participants will be recruited from parent meetings, the community at large, public bus system, and Facebook advertisements. (3) Due to the COVID-19 pandemic, assent/consent will be obtained online using a REDCap survey facilitated by a phone call with a research assistant to verify understanding of the study. When restrictions associated with the COVID-19 pandemic are eased, assent/consent will be obtained in-person using the following process. First, consent/assent will be obtained at either PI [name]’s research space at the School of Nursing or [name] research space at the Department of Psychology. Next, participants will complete surveys on tablet computers either PI [name]’s research space at the School of Nursing or [name] research space at the Department of Psychology. Parent/teen dyads will then be taken to Co-I [name]’s lab at the Department of Psychology where they will be seated in comfortable chairs in separate, quiet research rooms. Research assistants will then provide an overview of the physiological equipment, including the manner of attaching all recording sensors.

Consent Process

Indicate whether you will be obtaining consent:

Yes No

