We will recruit participants using an IRB-approved protocol. All participants will be required to give informed written assent/consent to participate in the project. Assent will be obtained from adolescent participants and consent will be obtained from the parents. No waiting period will be required between screening and consent. Trained research personnel will read, review, and discuss assent/consent forms with all potential participants prior to asking them to sign. It is anticipated that it will take approximately 30 minutes to complete the consent/assent process, but participants may take as long as they need to make a decision. Participants that seem

unsure about consent/assent will be encouraged to discuss it at home and contact us once a decision is made. If the candidate appears confused or indicates a lack of understanding, the interviewer will attempt to identify the misunderstanding and to explain the form again. Any candidate who still does not comprehend the form will be excluded from the study. We will ask questions to confirm understanding of the material covered in the assent/consent procedure (e.g., “Could you tell me what’s going to happen if you take part in the study?”). Trained research personnel will witness and date the signed forms. Assent/consent procedures will take place in a private room or office. PI [name] will keep assent/consent forms in a secured file cabinet within a locked room. At each study visit, study personnel will ask participants about their experience in the study (i.e. “How are things going for you in the study?”) and ask if they understand what is happening in the study (i.e. “Do you know why you’re here today?” or Do you have any questions about the study?”).

As consent is an ongoing process, subjects in the study may need to be re-consented/re-assented to inform them of new study information and reaffirm their willingness to continue participating in the research. National and local guidance recommends the use of the least burdensome approach for re-consenting/re-assenting a subject.^{42,43} The Office of Human Research Protections (OHRP) guidance for re-consent/re-assent will be followed,⁴⁴ which includes re-consenting/re-assenting active participants and verbal communication with documentation in the study record for participants who have already completed all study activities.

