We will not be providing individual results to participants’, however, general group results will be shared with participants at the end of the study, or as needed if the results may influence their decision to remain in the study.

Study Design, Procedures, and Timeline

(1) Study Design. We will use an exploratory 2-group pilot RCT to investigate the hypothesized effects of the TRUST intervention on depressive symptoms, QOL, sleep, stress management, medication adherence, and appointment keeping at 3 months and 6 months in comparison to the effects of a Depression Management Intervention.

(2 & 3) Research Procedures will include:

- a. **Recruitment and Informed Assent/Consent:** We will recruit participants using an IRB-approved protocol. All participants will be required to give informed written assent/consent to participate in the project. During the COVID-19 pandemic, we will be

obtaining assent/consent online via REDCap. Research assistants will read, review, and discuss assent/consent forms with all potential participants prior to asking them to sign. If the candidate appears confused or indicates a lack of understanding, the interviewer will attempt to identify the misunderstanding and to explain the form again. Any candidate who still does not comprehend the form will be excluded from the study. We will ask questions to confirm understanding of the material covered in the assent/consent procedure (e.g., "Could you tell me what's going to happen if you enroll in the study?"). Interviewers will witness and date the signed forms. Assent/consent procedures will take place in a private room or office. PI [name] will keep assent/consent forms in a secured file cabinet within a locked room. Participants will be enrolled in blocks of 10 dyads, using a block randomization scheme to assign each of the 10 dyads to either study group. Once a group of 5 is filled, weekly intervention sessions will begin.

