b. **Questionnaires:** Survey data will be collected using REDCap on a tablet computer. Measures used in the study are listed in the Table below. Due to restrictions associated with the COVID-19 pandemic, parents and adolescents will be asked to answer questions privately and at approximately the same time point on an electronic device connected to the internet in their homes. If, for example, only one electronic device is able to connect to the internet, the adolescent can complete the survey and then pass the device to the parent for survey completion. We are assessing families for internet access and device availability in the screening form. For families that do not have a device, we will mail them a tablet that they will mail back to us at the end of the study.

Study Variables, Measures, and Data Collection Points						
ADOLESCENT SURVEY						
Variable	Instrument	Title on Survey	B	3M	6M	
Depressive symptoms	Patient Health Questionnaire-8 ¹⁹	Depression Questions	X	X	X	
Quality of life	Youth Quality of Life-Short Form ²¹	Quality of Life Questions	X	X	X	
Sleep	PROMIS sleep disturbance-4 ²⁵ Children's Report of Sleep Patterns ²²	Sleep Questions More Sleep Questions	X X	X X	X X	
Stress management	Adolescent Lifestyle Questionnaire—stress management subscale ²³	How do you handle your stress?	X	X	X	
Medication adherence	Extent of Medication Adherence ²⁴	Medication Questions	X	X	X	
Appointment keeping	Hill-Bone Compliance Scale ²⁵	Appointment Questions	X	X	X	
Biologic Trust	Respiratory sinus arrhythmia ¹³	Not applicable—assessment in lab	X	X		
Behavioral Trust	Behavioral interaction assessment ¹⁴	Not applicable—assessment in lab	X	X		
Cognitive Trust	Children's General Trust Scale ²⁶	Children's Trust Questions	X	X	X	
Cognitive Trust	Parent Trust of Child Scale—Adolescent perceived ²⁷	Parental Trust Questions	X	X	X	
Relationship quality	Inclusion of Other in Self ²⁸	How close are you with your parent?	X	X	X	
Self-regulation	Positive and Negative Affect Schedule ²⁹	Emotion Questions	X	X	X	

Family cohesion	Brief Family Relationship Scale ³⁰	Family Relationship Questions	X	X	X
Rumination	Children's Response Style Questionnaire ³²	How do you handle sadness?	X	X	X
Self-efficacy	PROMIS Self-efficacy - Youth ³¹	Getting stuff done questions	X	X	X
Decentering	Experiences Questionnaire ³³	Self-awareness Questions	X	X	X
Demographics	Demographics questionnaire	Who are you?	X		
Perceived stress	Perceived Stress Scale-Peds ³⁴	Stress Questions	X	X	X

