COVID anxiety	COVID anxiety-5	COVID anxiety	X	X	X
Anxiety symptoms	PROMIS-25 Pediatric ¹⁹	Health Questions	X	X	X
Executive function	Pediatric Cognitive Function Short Form ³⁵	Thinking Questions	X	X	X
Parenting monitoring	Parental Monitoring Scale ³⁶	How much do your parents keep an eye on you?	X	X	X

PARENT SURVEY

Biologic Trust	Respiratory sinus arrhythmia ¹³	Not applicable—assessment in lab	X	X	
Behavioral Trust	Behavioral interaction assessment ¹⁴	Not applicable—assessment in lab	X	X	
Cognitive Trust	Parent Trust of Child Scale—Parent ²⁷	Parent's Trust of Child Questions	X	X	X
Relationship quality	Inclusion of Other in Self ²⁸	How close are you with your teen?	X	X	X
Relationship quality	Parent-Child Coercion Scale ³⁷	Parent-Child Communication Questions	X	X	X
Demographics	Demographic questionnaire	Who are you?	X		
Parenting style	Alabama Parenting Questionnaire-Shor ³⁸	Parenting Style Questions	X	X	X
Parent stress	PROMIS Perceived Stress Scale ³⁴	Stress Questions	X	X	X
General health	PROMIS-25 ¹⁹	General Health Questions	X	X	X

Note. B = baseline, 3M = 3 months, 6M = 6 months

We are also providing families with information about free or reduced cost internet access and free internet hot spots in the community (attached). Once restrictions associated with the COVID-19 pandemic are eased, in-person data collection will resume. Parent and adolescent will simultaneously answer questions on separate computers in a private room. This is intended to allow both to answer questions privately and to prevent parents from interfering with adolescent responses. During social distancing due to novel coronavirus-19, we will email a link to the questionnaire to participants. All materials will be assigned a unique number that will be used to link data over time. A master list linking the ID number to the participant's name will be kept in a password-protected computer file, in a locked office, at the local site. This list will be kept entirely separate from the data so that responses cannot be linked to the individual participant.

c. The risks associated with gathering information from participants by properly trained and supervised research assistants are low. Participants may experience discomfort by

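### Does the unstated starting point of the 3- and 6-month visits let the 3-month measurements fall before the last session?

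*Combined protocol and SAP*

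**What the plan says.** Study Design, Procedures, and Timeline sets outcomes at 3 and 6 months without naming a starting event. The note under the measures table only expands the labels: "Note. B = baseline, 3M = 3 months, 6M = 6 months".

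Item a of the same section enrols dyads in blocks of 10, "using a block randomization scheme to assign each of the 10 dyads to either study group", and adds: "Once a group of 5 is filled, weekly intervention sessions will begin". The same paragraph covers pandemic consent ("obtaining assent/consent online via REDCap") and does not exempt remote delivery from the fill rule. Item h gives both arms eight weekly sessions.

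On the in-person sequence, Setting has consent first, and then: "Next, participants will complete surveys on tablet computers". Consent Process says: "No waiting period will be required between screening and consent". The waiver section says pre-screening settles eligibility before a baseline visit is arranged.

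In the measures table, RSA and the behavioral interaction ("Not applicable—assessment in lab") are marked at baseline and 3 months only. Items f and g put both on pause until pandemic restrictions ease.

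The Study Procedures and Time Requirement table lists Visit 2 (3 months) after intervention week 8, and Visit 3 (6 months) last.

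**The concern.** A follow-up time needs an origin, and here the choice could matter because the plan builds in a variable wait. Suppose a dyad completes its baseline survey on the day of consent and then waits for four others in its arm. A 3-month visit counted from baseline could then fall part-way through the eight sessions, or in the extreme before the first. Visit 2 would measure dyads at different stages of treatment, although Aim 1 compares the arms at that visit.

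The survey measures are repeated at 6 months. RSA and the behavioral interaction, both Aim 2 mediators, are not, so a reading taken before session 8 would not be replaced. With 30 dyads, a few such readings would count.

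**Working it through.** The protocol gives no figure on this point to reproduce. The check asks how long a wait would cause trouble, how often it would occur, and whether the plan leads staff there.

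**1. The critical wait.** Three months is 365.25 / 4 / 7 = 13.04 weeks. Session 8 falls 7 weeks after session 1. On a baseline clock the slack is 13.04 − 7 = 6.04 weeks, taken as 6 below. If 3 months means 12 weeks, it is 12 − 7 = 5 weeks.

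**2. How many enrolments a dyad waits for.** Blocks of 10 and groups of 5 suggest a 5:5 split (inferred). There are 252 such allocations. Let the lag d be the number of enrolments from a dyad to the fifth dyad of its own arm:

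| d | 0 | 1 to 4 (each) | 5 | 6 | 7 | 8 | 9 |
|---|---|---|---|---|---|---|---|
| probability | 0.200 | 0.100 | 0.0992 | 0.0960 | 0.0881 | 0.0722 | 0.0444 |

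The mean lag is 0.1 × (1+2+3+4) + 5 × 0.0992 + 6 × 0.0960 + 7 × 0.0881 + 8 × 0.0722 + 9 × 0.0444 = 3.67.

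**3. How often the wait exceeds 6 weeks.** Assume exponential gaps between enrolments. The wait given lag d is then Gamma(d) at rate/52 per week, and P(wait > 6) = Σ p(d) × P(Gamma(d) > 6).

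At 52 per year (one per week) the tail for d = 1 to 9 is 0.002, 0.017, 0.062, 0.151, 0.285, 0.446, 0.606, 0.744 and 0.847. The weighted sum is 0.023 + 0.028 + 0.043 + 0.053 + 0.054 + 0.038 = 0.239.

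| Dyads per year | wait > 6 weeks | wait > 5 weeks (12-week reading) | wait > 19 weeks (6-month date before session 8) |
|---|---|---|---|
| 30 (assumed) | 0.457 | 0.513 | 0.034 |
| 52 (earlier study, Recruitment Methods) | 0.239 | 0.318 | 0.0003 |
| 104 (assumed) | 0.020 | 0.053 | 0.000 |

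With evenly spaced enrolment the first column becomes 50% at 30 per year, 20% at 52 and 0% at 104. These are shares of dyads to whom all the conditions in step 4 apply, not of all 30.

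**4. What has to be true for those shares to apply.**

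- *Months are counted from baseline.* No section says so. The time table puts Visit 2 after week 8, which a baseline clock breaks for long waits. The labels under the measures table have no origin, so they do not contradict that order.
- *Baseline is taken at enrolment, before the group exists.* Setting gives the order of steps within an in-person visit, not its date relative to group formation. The sentence in Consent Process removes a required delay; it does not prevent a family from being held. The waiver section has the baseline visit arranged after screening, and item a's enrolment in blocks of 10 can be read as cohort enrolment. None of this proves that families are held, but it is a fair reading, and the wait then shrinks or disappears.
- *The fill rule is in force.* Item h ties groups of about five to in-person sessions after restrictions ease. Its remote format is recorded material, which needs no group. Setting describes remote delivery differently ("intervention sessions will similarly be offered in a virtual (phone or video conferencing) format"), so a remote wait cannot be excluded.
- *For the mediators, the laboratory visits are running.* They are paused, and the totals in the Research Participant Compensation table ($75 each) cover three questionnaires and no laboratory payment.

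**5. The obvious alternative.** Counted from session 1, Visit 2 falls 13 − 7 = 6 weeks after session 8 whatever the wait, but baseline is older: 3.67 × 52 / rate gives 6.4, 3.7 and 1.8 weeks on average at 30, 52 and 104 per year. Suppose the baseline-to-3-month correlation r0 fades exponentially (an assumption). The effective correlation is r0 × E[r0^(wait/13)], and residual variance rises by the factor (1 − r_eff²)/(1 − r0²). For r0 = 0.5, r_eff is 0.373, 0.418 and 0.455, and the factors are 1.148, 1.101 and 1.057. Across r0 from 0.3 to 0.7 and the three rates, the rise is about 3% to 27%. It is nil if the correlation does not fade.

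**The case for a change.** The strongest case for a change is that the wait is a stated feature of the plan while the origin is not stated at all. The in-person text, read in sequence, puts consent, surveys and laboratory assessment together, and nothing in it waits for a group. The pauses do not remove the problem: in-person groups and laboratory measures would both return when restrictions ease, so the fill rule would operate just when the mediators are collected. One sentence of protocol text would settle the matter, with no added visit.

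Much of this stands. No origin or window is given, the arithmetic is sound, and the two laboratory mediators have no later visit. Setting and item h also describe remote sessions differently. What does not stand is the step from a missing origin to a plan that produces mistimed data. That step adds a baseline clock and an enrolment-day baseline, neither of which the plan states, and sets aside the one ordering it does give. Counts out of 30 would further assume that the whole trial runs in a mode that this version has suspended.

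**Conclusion.** No change is needed. This is missing detail, and the plan's own time table shows how to fill it: Visit 2 follows week 8. No stated rule gives a wrong result.

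On the unfavourable reading, about 24% of the dyads handled that way would be affected at 52 per year, with a range of 2% to 46% over assumed rates of 104 to 30. That rests on a borrowed rate, exponential gaps, a 5:5 split, enrolment-day baselines and a baseline clock. Even then the same rule applies to both arms, so no bias toward either is expected. The 6-month date would precede session 8 for 0.03% of dyads at 52 per year and 3.4% at 30. The laboratory mediators are the most exposed, but they are paused and may be collected on few of the 30 dyads, or none. In an exploratory pilot, choosing the origin can be left to those running the visits.

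The judgement would differ if trial documents showed months counted from an enrolment-day baseline while in-person groups and laboratory visits were running.

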Title: Pilot RCT to Evaluate the Effects of a Trust-Building Depression Management Intervention on Moderate Depressive Symptoms in Low-Income Adolescents

NCT: 03599141

Date IRB approved: 10/13/2022

PROTOCOL TITLE: Study comparing two depression management interventions for teens with depression

PRINCIPAL INVESTIGATOR:

[name], RN
Frances Payne Bolton School of Nursing
[contact]
[contact]

UH FACULTY ADVISOR: N/A

OTHER DEPARTMENTS INVOLVED IN THIS STUDY: Department of Psychology

VERSION NUMBER: 1.16

DATE: 09/28/2022

Study Comparing Two Depression Management Interventions for Teens with Depression

Objectives

(1) Our purpose is to test the Trust-building depression Self-Management Together (**TRUST**) intervention among adolescents with moderate depressive symptoms. Our premise is that trust can be learned, that increasing trust will improve self-regulation, and improved self-regulation will influence depression management behaviors, which will decrease depressive symptoms and increase quality of life (QOL). **The study aims are:**

Aim 1. Compare the effects of the TRUST intervention with a depression management intervention on depression management behaviors (sleep, stress management, medication adherence, appointment keeping) and health status (depressive symptoms, QOL) in adolescents with moderate depressive symptoms.

Aim 2. Assess whether the effects of the TRUST intervention on depression management behaviors (sleep, stress management, medication adherence, appointment keeping) and health status (depressive symptoms, QOL) are mediated by (respiratory sinus arrhythmia [RSA], behavioral interaction assessment, adolescent/parent trust self-reports, relationship quality, self-regulation, family cohesion, social support, decision making, self-efficacy, rumination, decentering).

Aim 3. Assess the effects of potential moderators (gender, race, perceived stress, parental monitoring, household income, parent level of education, parenting style, parent stress) on the relationship between the TRUST intervention and depression management behaviors and health status (depressive symptoms, QOL).

(2) **Hypothesis:** We hypothesize that variations in adolescent/ parent trust-building will predict response to the TRUST intervention and depression management behaviors as evidenced by change in depressive symptoms and QOL.

Background

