Inclusion and Exclusion Criteria

(1) **Screening.** Using an existing collaboration with the CMSD school system, participants will be recruited via advertisements in parent meetings at CMSD schools and social media. Candidates whose parents indicate interest by phone call, email, message, or completing an online prescreening tool will be contacted using an IRB approved script to recruit, screen, and enroll participants. Adolescents will complete the PHQ-8 measure of depressive symptoms over the phone or by REDCap link on a tablet computer. A PHQ8 score >8 and <20 will be considered for study inclusion. Screening the adolescent with the PHQ8 confirms that the adolescent currently has moderate depressive symptoms and will occur during the screening process, prior to consent/assent. We have requested a waiver of consent on page 7 for screening purposes.

(2) Inclusion (adolescent)	
1.	A Cleveland Metropolitan School District student
2.	Ages 14-17 years old
3.	Reports diagnosis of depression
4.	Reports moderate depressive symptoms (PHQ-8 score >8 and <20)
5.	Able to read, speak, and understand the English language
Inclusion (parent/guardian)	
1.	Female parent/guardian
2.	Able to read, speak, and understand the English language

(3) Exclusion (adolescent)	
1.	Current suicide risk
2.	Diagnosis with bipolar disorder, schizophrenia, or a personality disorder
3.	Sever behavioral problems that preclude group participation (as reported by parent)
4.	Family plans to move from the region within one year
Exclusion (parent)	
1.	Family plans to move from the region within one year

Number of Research Participants

(1) N = 30 adolescent/parent dyads
 (2) Single site study, N/A

Vulnerable Populations

(1) Vulnerable populations included are:

- Adults unable to consent**
- Minors (infants, children, teenagers)**
 - Wards of the state
 - Foster Children
- Pregnant Women**

- Neonates**
- Employees of CWRU or UHHS**
- Prisoners**
- Illiterate Individuals**
- Non-English Speaking**
- University Students**

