- h. **Intervention group protocol:** Due to restrictions associated with the COVID-19 pandemic, we will deliver both types of interventions in remote format wherein parents and adolescents will review video recordings of the materials, engage in exercises, and complete pre- and post-test to ensure engagement. Following the easing of restrictions associated with the COVID-19 pandemic, we will resume offering in-person sessions with parent-adolescents in groups of approximately five dyads. Each of eight 90-minute weekly sessions of the TRUST intervention will include both a trust-building topic and a depression management topic. Trust-building topics include honesty, reliability, and emotional connection.⁸ The honesty portion will include discussion and practice of disclosing personal truths and receptivity of others' disclosures. The reliability portion will include discussion and practice of making and keeping promises. The emotional connection portion will include discussion of adolescent-parent similarities and bonding activities like hugging and eye contact. The depression management portion will focus on sleep, stress management, medication adherence, and appointment keeping skills. The intervention will build depression management knowledge, set personal and dyad goals, and practice self-monitoring. Goal-setting and self-monitoring of progress are also forms of making and keeping promises, thus connecting and reinforcing the concepts of trust and depression management techniques. The **Depression Management group** will receive 8 sixty-minute weekly sessions that include the only the depression management training (sleep, stress management, medication adherence, appointment keeping) described above. Both intervention groups will be led by interventionists with health behavior change training.

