	Group 1	Group 2
Prescreening	5 minutes	5 minutes
Screening	30 minutes	30 minutes
Study Visit 1 (Baseline)	30 minutes	30 minutes
Intervention week 1	45 minutes	1 hours
Intervention week 2	45 minutes	1 hours
Intervention week 3	45 minutes	1 hours
Intervention week 4	45 minutes	1 hours
Intervention week 5	45 minutes	1 hours
Intervention week 6	45 minutes	1 hours
Intervention week 7	45 minutes	1 hours
Intervention week 8	45 minutes	1 hours
Study Visit 2 (3 months)	30 minutes	30 minutes
Study Visit 3 (6 months)	30 minutes	30 minutes
Total	8 hours 5 minutes	10 hours 35 minutes

ClinicalTrials.gov Information

Has this study been registered on ClinicalTrials.gov?

Yes. Provide the following:

- i. The ClinicalTrials.gov identifier: 00220503
- ii. Investigator/sponsor responsible for registering: [name]

No. Explain if there are plans to register or why registration is not required.

List of Data to be Collected

1. Indicate what identifiers you will collect

- Name
- Address
- Dates related to an individual (*birthdate*)
- Telephone number
- Fax number
- Email address

- Social security number
- Medical record number
- Health plan beneficiary number
- Account number
- Certificate/license number
- Any vehicle or other device serial
- Device identifiers or serial numbers
- Web URL
- Internet protocol (IP) address
- Finger or voice prints
- Photographic (video) images
- Other: Any characteristic that would uniquely identify the individual

Data Analysis Plan

(1) Statistical Analyses. Each participant will be assigned a unique identifier for tracking purposes and all raw data will be uploaded to the secure database in REDCap. We will explore all variables using descriptive statistics. To address the Aims 1-2, we will use a linear mixed effects model. To address Aim 3, we will apply usual mediation techniques.

Confidentiality of Specimens and Banking

Salivary specimens and cheek swabs are canceled due to Covid-19. Specimens collected prior to Covid-19 were handled as follows. Salivary specimens and cheek swabs will be collected and banked until full processing can occur. The specimens will be stored in the Frances Payne Bolton School of Nursing biomarker laboratory. Specimen testing is funded with internal monies; therefore, specimens will not be transferred to other researchers at this time.

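### The Data Analysis Plan assigns mediation methods to the moderator aim, names no moderation method, and sets no time ordering for mediators or moderators

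*Combined protocol and SAP*

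**What the plan says.** **Aims.** Objectives (1) sets out a sequence in which "increasing trust will improve self-regulation, and improved self-regulation will influence depression management behaviors", which then act on symptoms and quality of life. Aim 2 is the mediation aim and names eleven mediators. Aim 3 is the moderator aim and names eight moderators.

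**Methods.** Data Analysis Plan (1) promises descriptive statistics, a linear mixed effects model for Aims 1 and 2, and for Aim 3 states "we will apply usual mediation techniques". It says nothing about which visit supplies the mediator, the outcome or the moderator, or about baseline adjustment. No other section fills the gap.

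**Timing.** The table "Study Variables, Measures, and Data Collection Points" (Study Design, Procedures, and Timeline, item b) schedules all outcomes at baseline, 3 and 6 months. Study Design (1) sets the comparison "at 3 months and 6 months in comparison to the effects of a Depression Management Intervention". Item h describes "Each of eight 90-minute weekly sessions of the TRUST intervention", so the 3-month visit is the first assessment after treatment.

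**Size.** The target is "N = 30 adolescent/parent dyads". Blocks of ten dyads and groups of five imply about 15 per arm.

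**The concern.** There are two problems, and the first can be read directly from the text.

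1. **The methods do not match the aims.** Mediation methods are attached to the moderator aim, and no method for moderation is stated anywhere. A mediation analysis treats its third variable as something the randomised arm changes. A moderator analysis needs a variable fixed before the arm could act. Using one for the other answers a different question.

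2. **No ordering is imposed.** Four moderators have values after treatment, and seven mediators are reported at the same sittings as the outcomes. Self-regulation is measured with an affect schedule, rumination with a questionnaire on responses to sadness, and the outcome with the PHQ-8. An adolescent's mood on the day can move all three. A same-visit indirect effect can then be positive although the mediator does nothing.

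Aims 2 and 3 are two of the study's three aims, and larger studies are meant to build on this one. An indirect effect created by shared mood could be carried forward as the mechanism of the intervention.

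**Working it through.** The plan gives no effect size, SD, correlation or power figure for these aims, so there is nothing of its own to reproduce. The timing is checked row by row, and the size is worked under stated assumptions.

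**Step 1: timing against the aims**

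| Variables | Visits |
|---|---|
| All six outcomes (sleep, stress management, medication adherence, appointment keeping, depressive symptoms, QOL) | Baseline, 3, 6 months |
| Seven mediators: trust self-reports, relationship quality, self-regulation, family cohesion, self-efficacy, rumination, decentering | Baseline, 3, 6 months |
| Two mediators: RSA, behavioral interaction (both paused) | Baseline, 3 months |
| Two mediators: social support, decision making | No row in the table |
| Four moderators: perceived stress, parental monitoring (the "Parental Monitoring Scale"), parenting style, parent stress | Baseline, 3, 6 months |
| Four moderators: gender, race, household income, parent education | Baseline only, taking them to be on the demographic forms |

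Mediators: 7 + 2 + 2 = 11. Moderators: 4 + 4 = 8. Both match the aims.

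**Step 2: the Aim 3 sentence taken literally.** With baseline values, randomisation makes the arm-to-variable path zero apart from chance, so a mediation analysis has nothing to estimate. That covers the four demographic moderators entirely. For the other four, mediation can have content only with the 3- or 6-month values, which treatment may have altered.

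**Step 3: same-visit pairing (Aim 2).** Assume the arm shifts the mediator by a = 0.5 SD, the mediator has no effect on the outcome, and the same-visit residual correlation is r. With unit residual SDs the fitted mediator-to-outcome slope is b = r, so the spurious indirect effect is a × r:

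- r = 0.2: 0.5 × 0.2 = 0.10 SD
- r = 0.4: 0.5 × 0.4 = 0.20 SD
- r = 0.6: 0.5 × 0.6 = 0.30 SD

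In 4,000 simulated trials per setting with 15 per arm, the means were 0.101, 0.199 and 0.300. Requiring both paths to reach two-sided 0.05, false mediation was declared in about 5%, 15% and 25% of trials. The arm-to-mediator path was significant in only about 27%, which caps these rates.

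A second null makes the mediator purely a consequence of the outcome, with correlation 0.3, 0.5 or 0.7. False mediation at n = 30 was then 1.8%, 6.4% and 14.8% for a treatment effect of 0.5 SD, and 2.4%, 11.6% and 31.6% for 0.8 SD. At n = 200 the range was 17% to 98%, so this is bias that a larger trial would inherit.

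**Step 4: what a lag achieves.** Pair the 3-month mediator with the 6-month outcome.

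- *Adjusted for the 3-month outcome, no true mediation:* the mean indirect effect is about 0.00. Under the second null, false mediation is 0.4% to 1.5% at n = 30.
- *Adjusted for the 3-month outcome, true mediation completed by 3 months* (assumed path 0.6, so 0.5 × 0.6 = 0.30 SD): the estimate is 0.003 at n = 30 and 0.001 at n = 200. The real effect is missed.
- *Not adjusted for the 3-month outcome:* with an assumed 3-to-6-month carry-over of 0.5, the spurious effect halves but does not vanish: 0.5 × 0.2 × 0.5 = 0.05, 0.5 × 0.4 × 0.5 = 0.10, 0.5 × 0.6 × 0.5 = 0.15 SD. The true early effect also halves: 0.30 × 0.5 = 0.15 SD.

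So shared mood at r = 0.6 and genuine early mediation with path 0.6 give the same pair of answers: about 0.00 adjusted and 0.15 SD unadjusted. The lag helps, but neither version is sufficient alone.

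**Step 5: moderator measured after treatment (Aim 3).** Assume 15 per arm, a treatment effect of 0.50 SD, no true moderation by the baseline value, and an individual response that moves moderator and outcome together.

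| SD of individual response | False interactions, 3-month value | Treatment coefficient, 3-month value |
|---|---|---|
| 0 | 5.0% | 0.40 |
| 0.5 | 7.2% | 0.38 |
| 1.0 | 19.8% | 0.29 |

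With the baseline value, false interactions were 4.4% to 5.2% and the coefficient stayed close to 0.50.

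**The case against.** **The schedule is sound.** Measuring everything at three visits is not a fault. It supplies a baseline for every repeated moderator and a 3-to-6-month lag for every mediator that has a row. This stands: the gap is in the analysis text.

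**The plan never says it will do the wrong thing.** A reader might infer that same-visit pairing, or 3- and 6-month moderator values, are planned. The documents do not say so. A mixed model can take a lagged covariate, and the analysts may intend baseline moderators. This also stands. What remains is that nothing in the plan prevents either choice, and that the one sentence on Aim 3 names the wrong kind of method.

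**The mismatch may be a slip in numbering.** That is plausible. But swapping the labels would still leave moderation without a usable specification and mediation without an order.

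**The magnitudes are assumed.** True. Of the inputs, only the sample size comes from the documents. At r = 0.2 false mediation is no higher than 5%, and a moderator shifted equally in everyone gives no excess of false interactions.

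**A lag is no cure.** Correct, as Step 4 shows. It also leaves mediator-outcome confounding possible, and two follow-up visits cannot order a four-step chain.

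**This is an exploratory pilot.** No decision rule rests on Aims 2 or 3. That lowers the severity but does not remove the mismatch.

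**Conclusion.** The point holds in a limited form. The certain part is textual: mediation methods are assigned to the moderator aim, no moderation method is named, and no ordering or baseline-only rule appears.

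The conditional part is bias. If mediators and outcomes from the same survey are paired, the spurious indirect effect is the arm's effect on the mediator times the same-visit correlation, or 0.10 to 0.30 SD under the assumptions used. If post-treatment moderators are used, false interactions range from 5.0% to 19.8%, depending on how much individual response varies.

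Three stronger readings should be resisted:

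- That all moderators are exposed. Only four of eight are re-measured.
- That all mediators share visits with the outcomes. RSA and behavioral interaction have no 6-month value, so they can only precede the 6-month outcome. Social support and decision making have no instrument row, so timing cannot be judged.
- That a lagged estimate near zero shows there is no mediation. After adjustment for the 3-month outcome it may only mean that mediation was complete by 3 months.

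Severity is low: 30 dyads, exploratory, and no decision depends on the result.

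**What to change.** Amend Data Analysis Plan (1); no new data are needed.

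1. **Labels.** Assign mediation methods to Aim 2 and moderation methods to Aim 3.
2. **Aim 3.** Test an arm-by-moderator interaction using only each moderator's baseline value. This costs nothing.
3. **Aim 2.** Report the indirect effect through the 3-month mediator on the 6-month outcome, adjusted for baseline mediator and baseline outcome, with a bootstrap confidence interval. Show it both with and without adjustment for the 3-month outcome, and explain what each version can miss.
4. **Same-visit associations.** Label them descriptive.
5. **Gaps.** State that 3 to 6 months is the only lag for RSA and behavioral interaction, and say how social support and decision making will be measured or that they are dropped.

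The cost lies in Aim 2. The lagged analysis uses only dyads with both follow-ups and does not address the 3-month outcome. With adjustment for the 3-month outcome it misses mediation completed before 3 months; without it, same-visit correlation is not fully removed. With about 15 per arm, intervals will be wide either way.
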